#### 8.1.3 DEFINITION OF UNANTICIPATED PROBLEMS (UP)

Unexpected Events (UE) will be recorded on the UE/SAE log (*Appendix D*) and will include information including date of the event, when the study team was informed of this event, event details, when the IRB was notified, and whether the SAE Form was completed. The IRB will be notified of each UE that may occur during the study.

The Office for Human Research Protections considers unanticipated problems involving risks to participants or others to include, in general, any incident, experience, or outcome that meets all of the following criteria:

- Unexpected (in terms of nature, severity, or frequency) given (a) the research procedures that are described in the protocol-related documents, such as the IRB-approved research protocol and informed consent document; and (b) the characteristics of the participant population being studied;
- Related or possibly related to participation in the research
- Suggests that the research places participants or others at a greater risk of harm (including physical, psychological, economic, or social harm) than was previously known or recognized.

If an UE occurs the IRB will be notified and the study will be adjusted as needed to protect the health and safety of the participants. Depending on the nature of the UE, the research protocol, inclusion/exclusion criteria, and informed consent will be changed to reflect the possibility of this event reoccurring. During this time, no new participants will be recruited and the research procedures for currently enrolled participants will be stopped. Each UE will be recorded and reported throughout the study.

## 8.2 CLASSIFICATION OF AN ADVERSE EVENT

### 8.2.1 SEVERITY OF EVENT

All AEs will be graded for severity using the following guidelines.

- **Asymptomatic:** the participant is exhibiting no symptoms due to the event; no treatment needed.
- **Mild AE**– Event results in mild or transient discomfort, not requiring intervention or treatment; does not limit or interfere with daily activities (e.g., insomnia, mild headache).
- **Moderate AE** – Event is sufficiently discomforting so as to limit or interfere with daily activities; may require interventional treatment (e.g., fever requiring antipyretic medication). In the case of a moderate adverse event the medical advisor may recommend an over the counter medication.
- **Severe and undesirable AE** – Event results in significant symptoms that prevents normal daily activities; may require hospitalization or invasive intervention (e.g., anemia resulting in blood transfusion).

Changes in the severity of an AE will be documented with the Note to File document (*Appendix G*) and will be filed in the participant's folder.

### 8.2.2 RELATIONSHIP TO STUDY AGENT

The PI and Co-I will together determine whether an AE is associated with the study treatment. The event will be labeled associated if the event is temporally related to the administration of the therapy and no other factors can explain the event. The event will be labeled as not associated if the event is temporally independent of the study treatment and can be explained by external factors such as major life events.

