#### 8.5 STUDY HALTING RULES

If a seizure or any other Grade III adverse event occurs at the time of a study visit, a temporary hold will be placed over the study and further investigation will ensue. This could lead to stopping the study prematurely or continuing on with further safety measures in place. If it is found after investigation that the seizure was not related to the stimulation then the temporary hold of the study will be lifted. If, after investigation into the seizure or Grade III adverse event occurs, and there is found to be further well tested and documented safety measures that can be employed in the study to prevent further seizures or Grade III adverse events, then the temporary hold on the study will be lifted. If two seizures are witnessed during the study visits, the entire study will be stopped prematurely. These individuals would be referred for further medical attention. It is very unlikely that a seizure will occur, given that previous studies using tDCS in patients with depression and schizophrenia and previous studies in the lab using tACS (IRB14-1622, IRB14-3285) have had no seizures occur (Berlin et al., 2013, Brunelin et al., 2012). The study will also be stopped if other studies provide evidence that transcranial current stimulation has been associated with other, previously unrecognized, potentially harmful effects, either short-term or long-term.

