**APPENDIX B: AE LOG**

Participant ID	✓ if AE meets definition of serious*	Grade and Intensity	Date of Incident	Relationship to study device	Was Action Taken?	Action(s) Taken:	Outcome:	PI Initials / Date
		1. Asymptomatic 2. Mild 3. Moderate 4. Severe		1. Related 2. Possibly 3. Not Likely 4. Not Related			1. Recovered 2. Not Recovered 3. Recovered w/Sequel 4. Fatal 5. Unknown	
					Yes / No			
					Yes / No			
					Yes / No			
					Yes / No			
					Yes / No			

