## APPENDIX C: SAE REPORT FORM

Participant ID: \_\_\_\_\_

1. Location of SAE (e.g., clinic, home): \_\_\_\_\_
2. Age: \_\_\_\_\_
3. Gender: Male Female
4. SAE term (provide diagnosis): \_\_\_\_\_
- 4a. If diagnosis is not known, symptoms: \_\_\_\_\_
5. Date of onset: \_\_\_\_\_ (dd/mm/yyyy)
6. What is the severity grade of the serious adverse event?

Grade: 1: Mild

Grade 2: Moderate

Grade 3: Severe

Grade 4: Life-threatening

Grade 5: Death

7. Did the participant receive the investigational product or study intervention prior to this SAE?

Yes

No

N/A

- 7a. If yes, identify the investigational product or study intervention received prior to the SAE:

Investigational Product/Study Intervention

Dose\_\_\_\_\_

Units\_\_\_\_\_

Frequency\_\_\_\_\_

Start Date \_\_\_\_\_/\_\_\_\_\_/\_\_\_\_\_ (dd/mm/yyyy)

Stop Date \_\_\_\_\_/\_\_\_\_\_/\_\_\_\_\_ (dd/mm/yyyy)

Check if Ongoing

8. Action taken with investigational product/study intervention:

Continued

Lowered

- Interrupted
- Discontinued
- Increased
- N/A

9. Outcome of SAE:

- Ongoing at this time
- Resolved without sequelae
- Resolved with sequelae
- Death
- Present at death, not contributing to death

10. Date of resolution: \_\_\_\_\_ (dd/mm/yyyy) or

- Ongoing at end of study

11. Seriousness criteria? (Check all that apply)

- Life-threatening
- Required hospitalization or
- Prolongation of existing hospitalization
- Congenital anomaly
- Disabling/incapacitating
- Important medical event
- Fatal

If fatal: 11a. Date of death: \_\_\_\_\_ (dd/mm/yyyy)

11b. Primary cause of death: \_\_\_\_\_

11c. Was an autopsy performed?

- Yes
- No

12. Relationship to investigational product/study intervention:

- Related (Associated with the use of the study intervention. There is a reasonable possibility that the experience may have been caused by the study intervention.)
- Unrelated

13. If SAE is unrelated to investigational product/safety intervention, select all possible etiologies:

Concurrent illness, disease, or other external factors, specify:

---

Concurrent medication, specify:

---

Secondary study procedure, specify:

---

Accident, trauma, or other external factors, specify:

---

Other, specify:

---

14. Did the participant receive any relevant concomitant medications in response to the SAE?

Yes  
 No

14a. If yes, please specify: Name, Start and Stop date or On going

---

15. Did the participant receive any treatments/procedures in response to the SAE?

Yes  
 No

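### The relatedness rule in section 8.2.2 leaves two of four cases without a label and conflicts with the SAE form, so attribution of events to the device may be inconsistent

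*Combined protocol and SAP*

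**What the plan says.** Section 8.2.2 is the only place in the body of the protocol that defines relatedness. It gives two labels. An event is "labeled associated if the event is temporally related to the administration of the therapy and no other factors can explain the event". It is "not associated if the event is temporally independent of the study treatment and can be explained by external factors such as major life events". On who decides: "The PI and Co-I will together determine whether an AE is associated with the study treatment".

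Other parts of the same document use other standards:

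- **Appendix B (AE log)** offers four levels, "1. Related 2. Possibly 3. Not Likely 4. Not Related", and defines none of them. Section 8.1.1 says that the PI assesses the relationship entered on this log.
- **Appendix C (SAE form)** offers related or unrelated. It explains the first with the word associated and adds: "There is a reasonable possibility that the experience may have been caused by the study intervention".
- **Section 8.1.3** makes "Related or possibly related to participation in the research" one of the criteria that an unanticipated problem must meet.
- **Section 8.4** sets 24-hour and 48-hour reporting, to the IRB and the DSMB among others, for unexpected serious reactions that are suspected.
- **Section 8.5** says of a seizure during a visit: "If it is found after investigation that the seizure was not related to the stimulation then the temporary hold of the study will be lifted".

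No section says how these standards correspond.

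**The concern.** A relatedness rule should place every event somewhere, and should place it in the same category whichever form is in the assessor's hand. Section 8.2.2 does neither. Each label needs two conditions at once, so mixed cases drop out. The bar for associated, that no other factor can explain the event, is far above the bar on the SAE form, although both use the same word.

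The mixed case with a temporal link is easy to foresee. Section 2.3.1 lists headache among reported effects and says it is unclear whether stimulation causes these effects. Section 5.1 requires more than one year of illness and current antipsychotic doses held for at least four weeks. The AE report form (Appendix A) asks about baseline symptoms, concurrent conditions and concurrent medication, so assessors are prompted to look for other explanations.

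At stake is which events are attributed to the device, which meet the relatedness criterion for an unanticipated problem, and which serious events count as suspected reactions with a 24-hour or 48-hour clock.

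**Working it through.** The plan gives no figure on this point, so there is none to reproduce. The check enumerates the rule's cases and then compares the standards.

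**Step 1. Cases under 8.2.2.** Let T mean temporally related to stimulation, and E mean that another factor can explain the event. Associated requires T and not E. Not associated requires not T and E.

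| T | E | Label under 8.2.2 |
|---|---|---|
| yes | no | associated |
| no | yes | not associated |
| yes | yes | none |
| no | no | none |

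Two of the four combinations have no label, and no default is given for them.

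**Step 2. One event, four standards.** Take a headache after a session in a participant who also has another possible cause for it (T yes, E yes).

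- Section 8.2.2: no label. It cannot be associated, because another factor can explain it. It cannot be not associated, because it is not temporally independent.
- Appendix B: possibly or not likely could each be chosen, since neither is defined.
- Appendix C, if the event were serious: related, whenever causation by stimulation is a reasonable possibility.
- Section 8.1.3: the relatedness criterion is met if the event is judged possibly related.

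The conflict with Appendix C is direct: same word, different threshold. For Appendix B, 8.1.3 and 8.4 the fault is different. Section 8.2.2 has no intermediate category, and nothing links its labels to theirs.

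**Step 3. Who assesses.** Section 8.2.2 names the PI and Co-I together. Section 8.1.1 names the PI for the log entry. Section 10.4.3 lets the PI determine a participant's stimulation condition after an AE or SAE, so the PI's assessment may not stay blinded.

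**Step 4. How much the gap could matter.** The documents do not say how often a temporally related event also has another possible explanation. Call that share q, as an assumption. The share of temporally related events that 8.2.2 can label associated is then 1 − q:

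| Assumed q | Could be labelled associated (1 − q) | No label (q) |
|---|---|---|
| 10% | 90% | 10% |
| 30% | 70% | 30% |
| 50% | 50% | 50% |
| 80% | 20% | 80% |

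The table shows only how the result depends on q. It is not an estimate for this trial.

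**The case against.** The strongest reply is that little depends on the 8.2.2 label, and much of this stands.

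- **Capture is complete without it.** Section 8.1.1 has all AEs documented whatever their relationship to tACS, 8.1.3 has the IRB notified of each unexpected event, and 8.1.2 has all SAEs reported to the IRB. Under 8.6 the medical monitor reviews AEs in real time and the DSMB reviews them every six months.
- **Tolerability can be compared without it.** The stimulation adverse effects questionnaire follows every session, active or sham. Section 10 plans no table of related AEs.
- **The reporting criteria stand on their own.** Sections 8.1.3 and 8.4 state their own tests and do not refer to 8.2.2, so what is missing there is a link between the scales; the standards do not contradict each other.
- **Unlabelled does not mean not associated.** The AE log's two middle levels could hold the unlabelled cases. Section 8.2.2 also says if, not only if, although a definition is fairly read as setting the condition.

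Three stronger readings are therefore tempting but not supported:

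- *Device effects will be under-counted.* This does not follow, because capture does not depend on the label and assessors using the printed forms may record possibly or related.
- *Almost no event could be labelled associated.* This treats medication and chronic illness as an explanation for anything. Tingling, burning or itching under an electrode has no obvious competing cause, and 8.1.1 treats conditions noted at the initial session as baseline.
- *The rule makes it easier to lift a hold under 8.5.* Read literally, it does the opposite. Not associated requires temporal independence, which an event during a stimulation visit can hardly meet.

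The reply does not remove the two unlabelled cases, the conflict with Appendix C, the lack of any mapping between scales, or the difference in assessor.

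**Conclusion.** The concern holds as a point about classification. Section 8.2.2 leaves two of four combinations without a label and sets a threshold for associated that conflicts with Appendix C. If it is applied literally, attribution to the device may be inconsistent. Events that bear on reporting as unanticipated problems or suspected serious reactions may be under-classified.

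The conclusion rests on reading 8.2.2 as a definition and on the absence of any mapping elsewhere in the document. The number of events affected cannot be derived from the documents. Total AE and SAE capture, the between-arm comparison of questionnaire side effects and the primary AHRS analysis are not affected. The inconsistency should be corrected, since it concerns safety classification and costs little to remove.

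**What to change.** 1. Replace the 8.2.2 text with one defined relatedness scale that covers all four combinations of temporal link and other explanation. The AE log's four levels would serve once each is defined.
2. Use that scale in 8.1.1, 8.2.2 and Appendices B and C, with one named assessor arrangement throughout.
3. State which levels count as related for 8.1.3, for 8.4 and for any tabulation of related events. To agree with Appendix C and 8.1.3, these should include at least every level with a reasonable possibility of causation.
4. Reconcile the wording on relatedness in 8.5 with the chosen scale. This point proposes no halting rule.
5. Have AEs already logged re-graded on the new scale by an assessor who is still blinded. Because of 10.4.3, that may not be the PI for every event.

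The cost is a paragraph of protocol text, revised wording on two forms and re-grading of the existing log. The downside is that somewhat more events will be reported as possibly related.

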## 8.3 TIME PERIOD AND FREQUENCY FOR EVENT ASSESSMENT AND FOLLOW-UP

Medical monitor/Co-I will follow up with participants within one week of an AE.

## 8.4 REPORTING PROCEDURES

We will be adopting the following procedures for reporting procedures:

What Event is Reported	When is Event Reported	By Whom is Event Reported	To Whom is Event Reported
Fatal or life-threatening unexpected, suspected	Within 24 hours of initial receipt of information	Investigator	

● Local/internal IRBs, DSMB

serious adverse reactions			
Non-fatal, non-life-threatening unexpected, suspected serious adverse reactions	Within 48 hours of initial receipt of information	Study Coordinator	
 
• Local/internal IRBs/Institutional Officials, DSMB
 

Unanticipated adverse device effects	Within 10 working days of investigator first learning of effect	Investigator	
 
• Local/internal IRBs
 

Unanticipated Problem that is not an SAE	Within 7 days of the investigator becoming aware of the problem	Investigator	
 
• Local/internal IRBs/Institutional Officials,
 

All Unanticipated Problems	Within 30 days of the IRB's receipt of the report of the UP from the investigator.	IRB	
 
• OHRP
 

		Investigator 	
 
• External IRBs
 

#### 8.4.1 REPORTING OF PREGNANCY

Pregnancy tests will be administered at the beginning of the first day of stimulation and at each of the maintenance sessions to all women of child-bearing potential. A pregnancy test will also be administered prior to the sMRI scan to all women of child-bearing potential. There are no studies that suggest tACS would interfere with pregnancy. However, should a participant become pregnant during the study their participation will be immediately terminated and will be sent to consult with Co-I/ medical monitor.

#### 8.5 STUDY HALTING RULES

If a seizure or any other Grade III adverse event occurs at the time of a study visit, a temporary hold will be placed over the study and further investigation will ensue. This could lead to stopping the study prematurely or continuing on with further safety measures in place. If it is found after investigation that the seizure was not related to the stimulation then the temporary hold of the study will be lifted. If, after investigation into the seizure or Grade III adverse event occurs, and there is found to be further well tested and documented safety measures that can be employed in the study to prevent further seizures or Grade III adverse events, then the temporary hold on the study will be lifted. If two seizures are witnessed during the study visits, the entire study will be stopped prematurely. These individuals would be referred for further medical attention. It is very unlikely that a seizure will occur, given that previous studies using tDCS in patients with depression and schizophrenia and previous studies in the lab using tACS (IRB14-1622, IRB14-3285) have had no seizures occur (Berlin et al., 2013, Brunelin et al., 2012). The study will also be stopped if other studies provide evidence that transcranial current stimulation has been associated with other, previously unrecognized, potentially harmful effects, either short-term or long-term.

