*Risk of Injury and Discomfort:* Transcranial current stimulation has been used without any reports of serious side-effects for more than a decade. This stimulation mode has NOTHING to do with electroconvulsive therapy that applies many orders of magnitude higher stimulation current. Rather, transcranial current stimulation is so weak that it does not cause super-threshold activation of neurons ([name] and McCormick, 2010). In particular, tACS has been used without reports of any serious side-effects. Some participants report a transient mild tingling, burning, or itching underneath the electrodes and headache, but no other side effects have been noted. Importantly, it remains unclear if these mild side-effects were caused by the transcranial brain stimulation. In order to monitor these side-effects, we will be administering an adverse effects stimulation questionnaire (*Attachments 1 & 2*) after each stimulation session to document whether these effects were experienced. Research personnel present during these sessions will also check in with the participant periodically during the stimulation to see whether they are comfortable. If any side-effect occurs (rated by the participant as stronger than "moderate") or the participant is experiencing severe discomfort, the stimulation will be immediately stopped.

While not previously reported with tDCS or tACS in humans, there is a theoretical possibility that stimulation of neuronal circuits could lead to epileptic discharges. To minimize this occurrence, we screen and exclude patients with personal and family history of neurological conditions from the study. If abnormalities or a seizure is witnessed during the course of the study, the subject will be referred to a neurology clinic for further evaluation and treatment.

We have no evidence that our treatment paradigms will increase auditory hallucinations if not treated (receive the sham treatment), as participants, will be by definition, stable. If an enrolled patient shows signs of increase symptoms that were not apparent during enrollment, a referral to UNC Psychiatry will be made. [name], Co-I, will facilitate this process.

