#### 8.1.1 DEFINITION OF ADVERSE EVENTS (AE)

**Adverse Event:** An AE, as defined by the NIH, is any unfavorable changes in health, including /abnormal laboratory findings that occur in trial participants during the clinical trial or within a specified period following the trial.

All AEs including local and systemic reactions not meeting the criteria for “serious adverse events” will be captured on the appropriate CRF. In addition, the AE Interview will be completed by the study coordinator during each lab visit (see attachment). For any Adverse events reported, a clinician will evaluate and indicate the severity of the event(s). The AE report form (*Appendix A*) will be completed for any reported AE. The AE form includes the following: what is known about the therapy and previous reported side effects, if the AE occurred in temporal relation to the therapy, whether or not the AE improves or disappears when treatment is stopped, whether the AE is a worsening of baseline symptoms or related to a concurrent medical condition or medication use. Once complete, both of these forms will be given to the PI and the Co-I who will review, comment and sign the forms. Completed forms will be placed in the participant’s folder.

The study coordinator will document any AE occurrence on the AE log (*Appendix B*) which includes information such as the date of the AE, severity, relationship to the treatment (assessed by the PI), actions taken, and outcome(s). The log will be reviewed and initialed by the PI 72 hours after being completed. All AEs occurring during the clinical trial will be documented appropriately regardless of relationship to tACS. All AEs will be followed to adequate resolution and will be graded for severity and relationship to the study treatment. Any medical condition noted at the initial session will be considered as baseline and not reported as an AE.

All AEs will be graded for severity using the following guidelines.

- **Asymptomatic:** the participant is exhibiting no symptoms due to the event; no treatment needed.
- **Mild** Adverse Event– Event results in mild or transient discomfort, not requiring intervention or treatment; does not limit or interfere with daily activities (e.g., insomnia, mild headache).

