#### 8.1.2 DEFINITION OF SERIOUS ADVERSE EVENTS (SAE)

**Serious Adverse Event (SAE):** An SAE, as defined by the NIH, consists of adverse events that result in death, require either inpatient hospitalization or the prolongation of hospitalization, are life-threatening, result in a persistent or significant disability/incapacity or result in congenital anomaly/birth defect. Other important medical events, based upon appropriate medical judgment, may also be considered Serious Adverse Events if a trial participant's health is at risk and intervention is required to prevent an outcome mentioned.

All SAEs will be recorded on the Serious Adverse Events Form (*Appendix C*), documented in the UE/SAE log and reported to the IRB. The SAE Form will be completed by the study coordinator, and includes information relating to the onset and nature of the SAE, relationship to the study treatment, seriousness of the SAE, treatment required as a response to the SAE, and outcome. This form will be filed in the participant's binder at the resolution of the event. The study coordinator will complete the UE/SAE log (*Appendix D*) which includes information such as the date of the event, time at which the study team was informed of the event, details, when the IRB has been notified, and the date that the SAE Form was completed.

---

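### The Grade III hold trigger in 8.5 names no scale and no upper range, and the two numbered forms disagree on what level 3 means

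*Combined protocol and SAP*

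**What the plan says.** Section 8.5 sets the rule for a temporary, study-wide hold: "If a seizure or any other Grade III adverse event occurs at the time of a study visit, a temporary hold will be placed". The term Grade III appears three times in that section: in the trigger, in the investigation that follows, and in the condition for lifting the hold. No scale is cited at any of them, and none of them adds a phrase such as or higher.

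Sections 8.1.1 and 8.2.1 define four severity categories in words: asymptomatic, mild, moderate, and severe. None has a number. Severe, the top category, is described as follows: "Event results in significant symptoms that prevents normal daily activities; may require hospitalization or invasive intervention".

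Numbers appear only on two forms:
- The AE log in Appendix B, under a column headed Grade and Intensity, lists "1. Asymptomatic 2. Mild 3. Moderate 4. Severe".
- The SAE report form in Appendix C has five grades, among them "Grade 3: Severe", with life-threatening at 4 and death at 5.

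The two forms cover different events. Section 8.1.1 states: "The study coordinator will document any AE occurrence on the AE log". Section 8.1.2 states: "All SAEs will be recorded on the Serious Adverse Events Form".

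**The concern.** A halting rule should give the same answer whoever applies it. Here the answer depends on which form the reader has in hand. The log is the form on which every adverse event receives a number, and there a 3 is a Moderate event. The 8.2.1 example of a Moderate event is a fever treated with an antipyretic. The same reading passes over a Severe event, because that is a 4.

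The missing upper range is a second gap. Even a reader who takes the SAE form as the intended scale finds that the literal trigger stops at grade 3 and does not mention grades 4 and 5.

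At stake is the consistency of a study-wide safety threshold. The sample size, the model and the primary test are not affected.

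**Working it through.** No arithmetic applies and the plan gives no figure to reproduce. The check is to line up every severity scale in the document and apply the 8.5 wording literally to each.

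| Severity | 8.1.1 and 8.2.1 | AE log (Appendix B) | SAE form (Appendix C) |
|---|---|---|---|
| Asymptomatic | no number | 1 | not listed |
| Mild | no number | 2 | 1 |
| Moderate | no number | **3** | 2 |
| Severe | no number | 4 | **3** |
| Life-threatening | no separate category | no level above 4 | 4 |
| Death | no separate category | no level above 4 | 5 |

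The two numbered scales are one step apart because the log starts at asymptomatic and the SAE form starts at mild.

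**Reading A: Grade III means 3 on the AE log.** A Moderate event at a visit triggers the hold. A Severe event is a 4 and is not named. This covers serious as well as non-serious Severe events, because the log takes all adverse events and has a tick box for the serious ones. A life-threatening or fatal event can be logged no higher than 4, so it is not named either.

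**Reading B: Grade III means Grade 3 on the SAE form.** A Severe event triggers the hold. Grades 4 and 5 are not named, because 8.5 gives a single grade and no range. This form is also completed only for serious events. Section 8.2.1 says that a Severe event may need hospitalization, not that it must, so a Severe event can be non-serious. Such an event gets no SAE form, and its only number is the 4 on the log.

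**Reading C: Grade III means the third category in 8.2.1 by list order.** That is Moderate, the same result as Reading A.

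A seizure at a visit triggers the hold under every reading, because 8.5 names it separately. The difference therefore concerns other adverse events at visits. No literal reading yields the rule that a clinician would expect, namely Severe and everything above it.

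**The case against.** The strongest reply is that the context settles the meaning. By speaking of any other Grade III event, 8.5 classes a seizure with that grade, and the SAE form calls Grade 3 Severe. Sections 2.3.1 and 8.1 stop a single stimulation session only when participant-rated discomfort goes above moderate. It would be odd to halt the whole study at a level where one session may continue. This stands as evidence of intent, although the session rule concerns participant ratings and is therefore indirect. Severe or above is almost certainly what was meant.

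The second reply is that other provisions catch what the hold might miss. Section 2.3.1 lists only mild effects: "Some participants report a transient mild tingling, burning, or itching underneath the electrodes and headache, but no other side effects have been noted". A Severe event possibly related to stimulation would therefore very likely be handled as unexpected under 8.1.3, in which case "no new participants will be recruited and the research procedures for currently enrolled participants will be stopped". Section 8.4 sends fatal or life-threatening unexpected suspected reactions to the IRB and DSMB within 24 hours. Section 5.5 allows termination for unacceptable risk, and under 8.6 the medical monitor looks at adverse events as they arise. This also stands in large part, and it is why the practical reach is small.

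These provisions do not fully replace the hold. The 8.1.3 criteria require a judgement that the event is unexpected and at least possibly related, whereas the 8.5 trigger requires no causality judgement. The 24-hour row in 8.4 is a reporting duty limited to serious reactions. Section 5.5 is discretionary. The medical monitor in 8.6 decides on individual participants.

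The third reply is that an unneeded hold for a Moderate event errs on the safe side. That is fair, but it has a cost. Section 8.5 releases the hold for unrelatedness only where the event was a seizure. For another Grade III event, the release condition it states is that further safety measures have been found.

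A reader might go further and infer that the plan sets its halting threshold at Moderate, or that Severe and life-threatening events would go unmanaged. The documents support neither. The first ignores the seizure pairing and the SAE form, and the second ignores 8.1.3, 8.4, 5.5 and 8.6.

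**Conclusion.** The point holds as a low-impact correction to a safety threshold. Section 8.5 uses a grade that the protocol text does not define and gives no upper range, and the only two numbered scales disagree at level 3 by one severity category. Against the log, the rule names Moderate and omits every Severe event; against the SAE form, it omits life-threatening and fatal events.

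The conclusion rests on a literal reading of 8.5 and on the absence of any other grading scale in the supplied text. It does not assume that staff would misapply the rule; the likely intent is clear, but it is not written down. How often a hold would be wrongly placed or missed cannot be stated, because the documents give no rate of moderate or severe events at visits. A reader might try to size the risk by counting the conditions needed for a missed hold, with non-seriousness as one of them. That count does not work: on the log reading, serious Severe events are omitted too.

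**What to change.** In 8.5, replace Grade III adverse event(s) at all three places with *adverse event(s) graded Severe under 8.2.1, including any life-threatening or fatal event*. This ties the trigger to the protocol's own worded definition, makes the form numbers irrelevant to the rule, and supplies the missing upper range. Writing only Severe or worse under 8.2.1 would be weaker, because Severe is the top category there and nothing worse is defined.

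The cost is three phrases in one section. The separate seizure trigger stays as it is. Section 8.6 needs no edit, because its reference back to 8.5 mentions only the seizure. The statistical analysis does not change. Aligning the numbering of the AE log and the SAE form would be tidy but is optional, and the correction does not depend on it.
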